## Appendix 1 Schedule of Activities for Patients with Follicular Lymphoma (Dose-Escalation and Expansion) (cont.)

is lost to follow-up, or the patient withdraws consent. Every effort should be made to follow all serious adverse events considered to be related to any of the study treatment components or trial-related procedures until a final outcome can be reported.

ee The screening PET-CT scan must be performed within 35 days prior to Day 1 of Cycle 1.

ff Perform only for patients who have received at least two cycles of induction treatment.

gg If PET-CT scan is positive at EOI, perform at 12 months after initiation of induction treatment, within 14 days prior to treatment administration.

hh CT scan of the neck (if clinically indicated), chest, abdomen and pelvis. If contrast is medically contraindicated (e.g., patients with contrast allergy or impaired renal clearance), MRI scans of the chest, abdomen, and pelvis (and neck, if clinically indicated) and a non-contrast CT scan of the chest may be performed. Combined PET/CT scanners may be used to collect diagnostic CT scans but only according to the technical guidelines in the imaging manual. Screening CT scan must be performed within 35 days prior to Day 1 of Cycle 1.

ii Perform at 12, 18, and 24 months after initiation of induction treatment, within 14 days prior to treatment administration.

jj Perform only if not done within the previous 3 months.

kk Perform every 6 months.

ll Bone marrow biopsy and aspirate must be performed within approximately 3 months prior to Day 1 of Cycle 1.

mm For patients with bone marrow involvement at screening, a repeat assessment will be performed at EOI if there is radiologic evidence of a complete response, and during maintenance or at EOM if there is radiologic evidence of a complete response or if clinically indicated (e.g., if there is clinical suspicion of progressive disease in the bone marrow with no radiologic evidence of progression).

nn Refer to Section [4.3.2.3](#) and Section [4.3.2.5](#) for details on dosing and schedule.

oo Perform within 7 days prior to Day 1 of Cycle 3.

pp *Regimen will be defined based on available safety, tolerability, PK, and PD data.*

## Appendix 2 Schedule of Activities for Patients with DLBCL

	Screening a		Induction (6 Cycles; 28-Day Cycles)								EOI	Consolidation (6 months) c	EOC d	Post-Treatment FU Period (Q3M) e	Survival FU Period (Q3M) e
	D-28 to D-1	D-14 to D-1	Cycle 1 (±1 d)				Cycle 2 (±2 d)		Cycles 3-6 (±2 d)		After Last Induction Dose b		35 Days after Last Dose		
			D1	D5	D8	D15	D1	D15	D1	D15					
Informed consent f	x														
Demographic data	x														
Medical history	x														
ECOG Performance Status	x														
Vital signs g	x		x		x	x	x			x		x h	x i	x	
Height	x														
Weight and body surface area	x														
12-lead ECG	x		x j	x j						x k		x	x j	x	
Complete physical examination l,m	x														
Targeted physical examination m,n			Cycles 2 and 4								x	x i	x	x	
Ann Arbor, IPI	x														
B symptoms o	x														
β 2 microglobulin			x												
Hematology p		x	x q,r		x r	x r	x r	x	x r	x	x	x	x i	x	
Serum chemistry s		x	x q,r		x r	x r,t	x r	x t	x r	x t	x	x	x i	x	

**Appendix 2**  
**Schedule of Activities for Patients with DLBCL (cont.)**

	Screening a		Induction (6 Cycles; 28-Day Cycles)								EOI	Consolidation (6 months) c	EOC d	Post-Treatment FU Period (Q3M) e	Survival FU Period (Q3M) e
	D•28 to D•1	D•14 to D•1	Cycle 1 (±1 d)				Cycle 2 (±2 d)		Cycles 3•6 (±2 d)		After Last Induction Dose b		35 Days after Last Dose		
			D1	D5	D8	D15	D1	D15	D1	D15					
Coagulation (INR, aPTT [or PTT], and PT)		x													
Pregnancy test u		x									x		x		
Hepatitis B and C testing v	x														
Quantitative IgA, IgG, IgM			x								x	x w	x	x x	
PK sample for obinutuzumab			x y												
PK sample for rituximab			x y												
PK sample for idasanutlin			x y												
Whole blood for MRD z			x r				x				x	x aa	x		
Whole blood for lymphocyte immunophenotyping bb			x r			x r	x r			x r	x	x aa	x	x x	
Serum for MIC-1			x y	x y			x y,cc			x y,dd					
Optional peripheral blood sample for RCR ee			x	x											
Tumor tissue specimen (leftover tissue may be used for optional RCR specimen ff )	x ff		x gg												
Concomitant medications		x	To be recorded continually until end of treatment												
Adverse events hh		x	To be assessed continually hh												

**Appendix 2**  
**Schedule of Activities for Patients with DLBCL (cont.)**

	Screening a		Induction (6 Cycles; 28-Day Cycles)						EOI		Consolidation (6 months) c	EOC d	Post-Treatment FU Period (Q3M) e	Survival FU Period (Q3M) e
	D•28 to D•1	D•14 to D•1	Cycle 1 (±1 d)			Cycle 2 (±2 d)		Cycles 3•6 (±2 d)		After Last Induction Dose b		35 Days after Last Dose		
			D1	D5	D8	D15	D1	D15	D1					
PET-CT scan	x ii									x jj		x jj		
CT scan kk	x kk							x ll		x jj	x mm	x jj	x nn	
Bone marrow biopsy and aspirate	x oo									x jj,pp	x pp	x jj,qq		
Study treatment administration	Obinutuzumab rr			x		x	x	x		x				
	Rituximab rr			x				x		x		x		
	Idasanutlin rr			D1•D5				D1•D5		D1•D5			x ss	
New anti-lymphoma treatment													x	x
Survival follow-up														x

CT = computed tomography; D = day; Discont. = discontinuation; ECOG = Eastern Cooperative Oncology Group; eCRF = electronic Case Report Form; EOC = end of consolidation; EOI = end of induction; FU = follow-up; IPI = International Prognostic Index; MRD = minimal residual disease; MIC = macrophage inhibitory cytokine-1; MRI = magnetic resonance imaging; PET = positron emission tomography; PK = pharmacokinetic; Q3M = every 3 months; RCR = Roche Clinical Repository; wk = week.

Notes: On treatment days, *all* assessments should be performed prior to dosing, unless otherwise specified.

Assessments shaded in gray should be performed as scheduled, but the associated data do not need to be recorded on the eCRF (except in the case of an adverse event).

a The screening period starts with the signing of the Informed Consent Form. Results of standard-of-care tests or examinations performed prior to obtaining informed consent and within the defined window may be used as screening and baseline assessments; such tests do not need to be repeated for screening purposes.

b EOI will be treatment completion visit. EOI assessments should be performed 6•8 weeks after Day 1 of the last induction cycle. As an exception, patients who discontinue induction treatment prematurely because of an adverse event may undergo EOI assessments 4•8 weeks after their last dose of study treatment.

## Appendix 2

### Schedule of Activities for Patients with DLBCL (cont.)

- c Consolidation treatment should start 8 weeks ( $\pm 1$  week) after Day 1 of the final cycle of induction and will continue until disease progression or unacceptable toxicity for up to 8 months.
- d Patients who complete consolidation treatment or discontinue consolidation treatment prematurely will undergo assessments at the EOC.
- e Patients who complete treatment or discontinue treatment for reasons other than disease progression will undergo assessments every 3 months during the post-treatment FU period, which will continue until disease progression, the start of new anti-lymphoma treatment, or the end of the study, whichever occurs first. The first post-treatment FU visit is 3 months after the EOI visit. Patients who experience disease progression will undergo limited assessments every 3 months during the survival FU period, which will continue until the end of the study. The end of the study is defined as the time when all enrolled patients with FL have completed or discontinued study treatment and all enrolled patients with DLBCL have been followed for at least 1 year after they have completed or discontinued study treatment.
- f Informed consent must be documented before any study-specific screening procedure is performed.
- g Vital signs include respiratory rate, pulse rate, body temperature, and systolic and diastolic blood pressures while the patient is in a seated position. For obinutuzumab infusions: For the first cycle and for patients who experience an infusion-related reaction, vital signs will be measured prior to the infusion, every 15 ( $\pm 5$ ) minutes for the first 90 minutes of the infusion, and then every 30 ( $\pm 10$ ) minutes until 1 hour after completion of the infusion. For the second and subsequent cycles, vital signs will be measured every 30 minutes during the infusion, except in patients who had experienced an infusion-related reaction during a prior infusion.
- h Perform only for patients who will not be receiving consolidation treatment.
- i Vital signs will be measured, a targeted physical examination will be performed, and hematology and serum chemistry will be assessed during consolidation every 2 weeks during the first month, every month until EOC. For rituximab infusions: Vital signs monitoring during infusion should be determined as per local label.
- j All ECGs should be collected prior to and 6 hours after idasanutlin administration or after obinutuzumab/*rituximab* administration, whichever occurs later. For Cycle 1 Day 5, perform ECG 6 hours post idasanutlin administration only if patient is still at clinic.
- k All ECGs should be collected prior to and 6 hours after idasanutlin administration or after obinutuzumab/*rituximab* administration, whichever occurs later. ECG will be performed as described on Cycles 4, Days 1 and 5 only. For Cycle 4 Day 5, perform ECG 6 hours post idasanutlin administration only if patient is still at clinic.
- l Includes evaluation of the head, eyes, ears, nose, and throat and the cardiovascular, dermatological, musculoskeletal, respiratory, gastrointestinal, genitourinary, and neurological systems. Record abnormalities observed at baseline on the General Medical History and Baseline Conditions eCRF.
- m As part of tumor assessment, the physical examination should include evaluation for the presence of enlarged nodes, palpable hepatomegaly, and splenomegaly. This information will be recorded on the appropriate tumor assessment eCRF.

## Appendix 2

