## **Investigational Medicinal Products**

### **Test Product (Investigational Drug)**

*Obinutuzumab will be administered by intravenous infusion at an absolute (flat) dose of 1000 mg on Days 1, 8, and 15 of the first cycle and on Day 1 of each subsequent cycle during induction treatment, and on Day 1 of every other month (i.e., every 2 months) for 24 months during maintenance treatment (eligible patients with FL only) or for 6 months during consolidation treatment (eligible patients with DLBCL only).*

*Rituximab will be administered by intravenous infusion at a dose of 375 mg/m^2 on Day 1 of Cycles 1•6 during induction treatment and on Day 1 of every other month (i.e., every 2 months) for 6 months during consolidation treatment (eligible patients with DLBCL only).*

*Idasanutlin tablets will be taken once daily by mouth, approximately 15 minutes after eating a meal and with water, on Days 1•5 of Cycles 1•6 (or Cycles 2•6 for the bridging cohorts in FL patients and in the expansion phase if this regimen is chosen), followed by 6 months of post-induction treatment. The starting dose will be 100 mg during the dose-escalation phase. The RP2D with the selected regimen will be administered during the expansion phase. The dose and regimen for post-induction treatment will be determined by the Sponsor after review of all relevant data.*

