### **3.1.3 Expansion Phase (Part 2)**

The expansion phase is designed to further assess the safety and efficacy of obinutuzumab in combination with idasanutlin at the RP2D *with the selected regimen in patients with R/R FL and of rituximab in combination with idasanutlin at the RP2D in patients with R/R DLBCL*. Approximately 80 patients (40 patients with R/R FL and 40 patients with R/R DLBCL) will be enrolled during the expansion phase and treated as described below. *The start of the expansion phase may not happen simultaneously for the two indications.*

All patients will receive 6 cycles of induction treatment, administered in 28-day cycles, as outlined in [Table 6](#). Patients with FL who achieve a CR or PR at the EOI will receive maintenance treatment with obinutuzumab and idasanutlin. *Patients with DLBCL who achieve a CR or PR at the EOI will receive consolidation treatment with rituximab and idasanutlin. Post-induction treatment should start 8 weeks ( $\pm 1$  week) after Day 1 of the final cycle of induction and will continue until disease progression or unacceptable toxicity for up to 2 years for maintenance treatment and 6 months for consolidation treatment (see [Table 7](#)).*

*Patients with DLBCL who achieve a CR based on modified Lugano 2014 criteria at the end of induction (defined as within 6-8 weeks after the start of the last cycle of study treatment) are allowed to proceed to hematopoietic stem cell transplantation if deemed appropriate by the investigator. Such patients will be followed for disease progression and survival.*

The schedules of assessments are provided in [Appendix 1](#) and [Appendix 2](#), and a study schema is provided in [Figure 6](#).

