**Table 7 Post-Induction Treatment for the Expansion Phase**

Post-Induction Treatment	
Patients with FL	Maintenance treatment consisting of the following: 
 
• Obinutuzumab 1000 mg IV every 2 months for 24 months
 
• Idasanutlin for 6 months a
 

Patients with DLBCL	Consolidation treatment consisting of the following: 
 
• Rituximab 375 mg/m^2 IV every 2 months for 6 months
 
• Idasanutlin for 6 months a
 

DLBCL = diffuse large B-cell lymphoma; FL = follicular lymphoma; IV = intravenous.

a Dose and regimen to be determined by the Sponsor after review of all relevant data. The dose for maintenance/consolidation will not exceed the dose the patient received during induction.

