  - qq *For patients with bone marrow involvement at screening, a repeat assessment will be performed at EOI if there is radiologic evidence of a complete response.*
  - rr Refer to Section 4.3.2.3 and Section 4.3.2.5 for details on dosing and schedule.
  - ss *Regimen will be defined based on available safety, tolerability, PK, and PD data.*

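### Appendix 2 footnote c caps DLBCL consolidation at 8 months; its own column header, Section 3.1.3, Table 7 and the synopsis all say 6 months

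*Combined protocol and SAP*

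**What the plan says.** Appendix 2, footnote c, sets the start of consolidation at eight weeks (plus or minus one) from the first day of the last induction cycle. It then says that treatment "will continue until disease progression or unacceptable toxicity for up to 8 months".

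The other statements of the duration in the current protocol are:

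- **Appendix 2, column header carrying marker c**, on all three pages of the table: "Consolidation (6 months" (the closing bracket and the marker follow).
- **Section 3.1.3**, with the same start point and stopping conditions: "for up to 2 years for maintenance treatment and 6 months for consolidation treatment".
- **Table 7, rituximab**: "IV every 2 months for 6 months".
- **Table 7, idasanutlin**: "Idasanutlin for 6 months".
- **Synopsis, Investigational Medicinal Products, rituximab**: "i.e., every 2 months) for 6 months during consolidation treatment (eligible patients with DLBCL only".
- **Synopsis, Investigational Medicinal Products, idasanutlin**: "followed by 6 months of post-induction treatment".

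For dosing, Appendix 2 footnote rr says: "Refer to Section 4.3.2.3 and Section 4.3.2.5 for details on dosing and schedule". Section 4.3.2.3 gives the two-monthly rituximab interval but no duration. Section 4.3.2.5 sends the reader back to Section 3, which says 6 months.

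**The concern.** The footnote contradicts the header it is attached to, and it is an operative limit on how long patients may receive investigational drugs. A site working from the schedule of activities could follow it in good faith.

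Three things depend on when consolidation ends:

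- exposure to rituximab and idasanutlin;
- the timing of the end-of-consolidation (EOC) visit, which Appendix 2 places 35 days past the final dose and which supplies the PET-CT for the exploratory CR-at-EOC endpoint (Section 2.2.3);
- the start of the one-year DLBCL follow-up in the end-of-study definition (Section 3.2), which runs from completion of treatment including consolidation.

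If sites read the cap differently, the first two would differ between patients for no clinical reason.

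**Working it through.** **Step 1: compare the statements.** Footnote c says 8 months. The Appendix 2 header, Section 3.1.3, both drug rows in Table 7 and both drug entries in the synopsis say 6. The discrepancy is 8 − 6 = 2 months. The cross-references in footnote rr lead only to 6.

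**Step 2: try to reproduce the 8.** One possibility is that 8 months was counted from Day 1 of the last induction cycle. With 1 month = 30.44 days:

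- earliest start: 7 weeks = 49 days; 49 / 30.44 = 1.61 months; 1.61 + 6 = 7.61 months
- latest start: 9 weeks = 63 days; 63 / 30.44 = 2.07 months; 2.07 + 6 = 8.07 months

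This may be where the figure came from, but it does not fit the sentence. Footnote c states when treatment starts and then how long it continues. Section 3.1.3 uses the same construction with 6.

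**Step 3: size the effect.** Take rituximab every 2 months from consolidation month 0. EOC is the last infusion plus 35 days, and 35 / 30.44 = 1.15 months. The plan does not say whether an infusion is given in the end month, so both conventions are shown.

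| Cap | End month | Infusions at months | Number | EOC (month) |
|---|---|---|---|---|
| 6 months | excluded | 0, 2, 4 | 3 | 4 + 1.15 = 5.15 |
| 6 months | included | 0, 2, 4, 6 | 4 | 6 + 1.15 = 7.15 |
| 8 months | excluded | 0, 2, 4, 6 | 4 | 6 + 1.15 = 7.15 |
| 8 months | included | 0, 2, 4, 6, 8 | 5 | 8 + 1.15 = 9.15 |

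- Same convention for both caps: 4 − 3 = 1 or 5 − 4 = 1 extra infusion. EOC moves by 7.15 − 5.15 = 2 or 9.15 − 7.15 = 2 months.
- End month included for 6 but excluded for 8: 4 − 4 = 0 extra infusions and no shift in EOC.

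The EOC figures assume that rituximab is the last drug given. Extra idasanutlin cannot be computed, because Table 7 footnote a leaves its post-induction dose and regimen to be decided.

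**Step 4: who is affected.** Section 3.1.1 offers DLBCL consolidation in the expansion phase. Section 3.1.3 restricts it to patients in CR or PR at the end of induction and plans approximately 40 DLBCL patients. About 40 is therefore a ceiling.

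**The case against.** The contradiction itself is hard to dispute; the case on the other side concerns certainty and consequence.

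- **The digit may be misread.** The finding rests on a single machine-read character, and 8 is not repeated anywhere as a duration of consolidation. The text has character errors elsewhere, such as EO1 for EOI in Sections 3.3.6.3, 4.4 and 4.5.5.2. Those errors confuse I with 1, not 6 with 8, so they prove nothing about this digit. A misread still cannot be excluded from the text alone. This stands, and it is why confidence is medium and the source check comes first.
- **Other text contains the error.** The header and the cross-references point to 6, and the sponsor must still set the idasanutlin regimen, which is another chance to notice the mismatch. This makes extra treatment unlikely, but it does not remove a written cap that permits it.
- **The endpoint effect is small.** CR at EOC is exploratory, limited to patients PET-positive at the end of induction, and timed from the last dose, so its definition survives. At the CR rate of 55% assumed in Section 6.1, 40 × 0.55 = 22 patients would be in CR and about 18 would not, and any of those 18 without a PR would receive no consolidation. Patients in CR may also leave for transplant. All of this stands and supports a minor rating.
- **The restriction to expansion patients is partly inferred.** Section 3.1.1 says that they may be eligible, without saying only they are. The synopsis also mentions obinutuzumab consolidation in DLBCL, although DLBCL patients receive obinutuzumab only in dose escalation. However, Section 2.2.3 labels the EOC endpoint as expansion only, and Section 3.1.2.2 and Tables 2 and 3 give no DLBCL consolidation in dose escalation.
- **The lower bound of zero needs mixed counting.** That is correct: under one consistent convention the answer is one extra infusion.

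**Conclusion.** The concern holds. Appendix 2 footnote c is wrong as written: it exceeds by 2 months the limit given everywhere else. The practical size is 0 to 1 extra rituximab infusion (1 if the end month is treated alike for both durations). The EOC visit moves by 0 or 2 months if rituximab is the last drug given, and the idasanutlin excess is unknown. The conclusion assumes that the digit in the source PDF is indeed 8. Severity is minor, since no primary analysis, sample-size figure or stopping rule depends on it.

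**What to change.** Check the digit in Appendix 2 footnote c against the source PDF. If it reads 8, change the cap to 6 months so that it matches the column header, Section 3.1.3, Table 7 and the synopsis. The cost is one digit in one footnote.

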## Appendix 1 Schedule of Activities for Patients with Follicular Lymphoma (Dose-Escalation and Expansion) (cont.)

- 
- a The screening period starts with the signing of the Informed Consent Form. Results of standard-of-care tests or examinations performed prior to obtaining informed consent and within the defined window may be used as screening and baseline assessments; such tests do not need to be repeated for screening purposes.
- b Patients who complete maintenance treatment or discontinue maintenance treatment prematurely will undergo assessments at EOM.
- c EOI assessments should be performed 6•8 weeks after Day 1 of the last induction cycle. As an exception, patients who discontinue induction treatment prematurely because of an adverse event may undergo EOI assessments 4•8 weeks after their last dose of study treatment.
- d Patients who complete treatment or discontinue treatment for reasons other than disease progression will undergo assessments every 3 months during the post-treatment FU period, which will continue until disease progression, the start of new anti-lymphoma treatment, or the end of the study, whichever occurs first. The first post-treatment FU visit is 3 months after the EOI visit for patients who do not receive maintenance treatment and 3 months after the last dose for patients who receive maintenance treatment. Patients who experience disease progression will undergo limited assessments every 3 months during the survival FU period, which will continue until the end of the study. The end of the study is defined as the time when all enrolled FL patients have completed or discontinued study treatment and all enrolled DLBCL patients have been followed for at least 1 year after they have completed or discontinued study treatment.
- e Informed consent must be documented before any study-specific screening procedure is performed.

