### Schedule of Activities for Patients with DLBCL (cont.)

treatment. After this period, the Sponsor should be notified if the investigator becomes aware of any serious adverse event that is believed to be related to prior study treatment (see Section 5.6). An exception is made for Grade 3–4 infections (related and unrelated) *in patients who received obinutuzumab*, which should be reported until up to 2 years after the last dose of *obinutuzumab*. The investigator should follow each adverse event until the event has resolved to baseline grade or better, the event is assessed as stable by the investigator, the patient is lost to follow-up, or the patient withdraws consent. Every effort should be made to follow all serious adverse events considered to be related to any of the study treatment components or trial-related procedures until a final outcome can be reported.

- ii The screening PET-CT scan must be performed within 35 days prior to Day 1 of Cycle 1.
- jj Perform only for patients who have received at least two cycles of induction treatment.
- kk CT scan of the neck (if clinically indicated), chest, abdomen and pelvis. If contrast is medically contraindicated (e.g., patients with contrast allergy or impaired renal clearance), MRI scans of the chest, abdomen, and pelvis (and neck, if clinically indicated) and a non-contrast CT scan of the chest may be performed. Combined PET/CT scanners may be used to collect diagnostic CT scans, but only according to the technical guidelines in the imaging manual. Screening CT scan must be performed within 35 days prior to Day 1 of Cycle 1.
  - ll *Perform within 7 days prior to Day 1 of Cycle 3.*
  - mmm *Perform 4 months after initiation of consolidation treatment.*
  - nn Perform a CT scan 3 and 6 months after EOI visit, and every 6 months thereafter.
  - oo Bone marrow biopsy and aspirate must be performed within approximately 3 months prior to Day 1 of Cycle 1.
  - pp For patients with bone marrow involvement at screening, a repeat assessment will be performed at *the EOI, during consolidation, or at the EOC whenever there is radiologic evidence of a complete response or if clinically indicated (e.g., if there is clinical suspicion of progressive disease in the bone marrow with no radiologic evidence of progression). Additional bone marrow assessments may be performed at the discretion of the investigator.*

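### Appendix 2 counts DLBCL follow-up visits and CTs from the end of induction even for consolidated patients, so the first of them fall during treatment and CT spacing after consolidation depends on the last-dose date

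*Combined protocol and SAP*

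**What the plan says.** Appendix 2 (DLBCL schedule) sets the follow-up calendar in three footnotes.

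- Footnote b, on the EOI visit: "EOI will be treatment completion visit". It continues: "EOI assessments should be performed 6•8 weeks after Day 1 of the last induction cycle".
- Footnote e, on visits: "The first post-treatment FU visit is 3 months after the EOI visit".
- Footnote nn, on CTs in the post-treatment column: "Perform a CT scan 3 and 6 months after EOI visit, and every 6 months thereafter".

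The same appendix provides for consolidation. Footnote c says "Consolidation treatment should start 8 weeks" (plus or minus 1 week) after Day 1 of the last induction cycle. Table 7 gives rituximab "IV every 2 months for 6 months", with idasanutlin also for 6 months on a schedule still to be set. Footnote mm adds a CT: "Perform 4 months after initiation of consolidation treatment". The EOC visit is 35 days after the last dose, and both the CT and the PET-CT rows are marked there (footnote jj).

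Appendix 1 footnote d (FL) separates the two situations. The first follow-up visit is counted from EOI for patients without maintenance, and is "3 months after the last dose for patients who receive maintenance treatment".

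**The concern.** Footnote e opens by reserving post-treatment follow-up for patients who have finished or stopped treatment, and Section 3.1.6 says the same. The EOI anchor then places the first such visit inside consolidation. The description of EOI in footnote b is also untrue for these patients.

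A site can read this in two ways. It can carry out the EOI + 3 and EOI + 6 month CTs during consolidation, in addition to the month-4 and EOC scans. Or it can treat any of those dates that fall before the end of treatment as passed. On either reading the CT dates after consolidation stay fixed to EOI, so the interval after the EOC scan is set by when the last dose happened to fall. Section 6.4.3 dates PFS, EFS and DFS from investigator-read CTs. Uneven scan spacing within one cohort shifts the recorded relapse dates of the responders who were consolidated.

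**Working it through.** The plan gives no figure for this, so the check is calendar arithmetic with 1 month = 30.44 days.

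Inputs:
- EOI visit: 6 to 8 weeks after Day 1 of the last induction cycle (footnote b).
- Consolidation start: 7 to 9 weeks after that day (footnote c).
- Offset d = consolidation start minus EOI: from 7 − 8 = −1 week to 9 − 6 = +3 weeks, that is −0.23 to +0.69 months.
- EOC scan: last dose + 35 days, and 35 / 30.44 = 1.15 months.
- Follow-up CTs: EOI + 3, 6, 12, 18 months (footnote nn).
- L = month of consolidation in which the last dose falls. This is an assumption. A 2-monthly antibody over 6 months and an unfixed idasanutlin schedule make months 4 to 6 plausible. Month 8 is added because footnote c allows up to 8 months.

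Step 1, the first follow-up visit and CT. Their position in consolidation is 3 − d, from 3 − 0.69 = 2.31 to 3 + 0.23 = 3.23 months. Even with the last dose at month 4, this is before the last dose under every permitted timing.

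Step 2, the second follow-up CT. Its position is 6 − d = 5.31 to 6.23 months, near the end of a 6-month consolidation. Read literally, the patient has CTs at about months 3, 4 and 6 and at EOC.

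Step 3, the interval after the EOC scan. The EOC scan falls at EOI + d + L + 1.15; the next CT is the first of EOI + 6, 12, 18 after it.

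| Last dose (L) | EOC scan, months after EOI | Next CT | Interval, months |
|---|---|---|---|
| 4 | 4.92 to 5.84 | EOI + 6 | 0.2 to 1.1, then 6 to EOI + 12 |
| 5 | 6.15 to 6.84 (d from 0 to 0.69) | EOI + 12 | 5.2 to 5.9 |
| 6 | 6.92 to 7.84 | EOI + 12 | 4.2 to 5.1 |
| 8 | 8.92 to 9.84 | EOI + 12 | 2.2 to 3.1 |

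There is one exception at L = 5. With EOI at week 8 and consolidation starting at week 7, the EOC scan is at EOI + 5.92, the EOI + 6 CT follows 0.1 months later, and the next is 6 months after that.

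Step 4, the comparison. Without consolidation, the EOI scan is followed by CTs 3 and 6 months later, then six-monthly.

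**The case against.** A reader might infer that consolidated patients have no CT for 5 to 7 months after treatment ends. The documents do not support that: CT and PET-CT are due at EOC, 1.15 months after the last dose. Nor does any tested timing give a 7-month wait after EOC, because when the last dose is early the EOI + 6 CT comes next.

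The comparison also narrows when both groups are counted from the last dose. Without consolidation, the last dose is Day 5 of Cycle 6. The EOI scan is then 38 to 52 days later (1.25 to 1.71 months) and the next CT is at 4.25 to 4.71 months. With consolidation and L = 6, the scans are at 1.15 months and at 6 − d = 5.31 to 6.23 months. For the same EOI week, the second scan is about 1.1 to 1.5 months later. That is modest, but the third scan is then 3 months further on without consolidation and 6 months further on with it.

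A reader might also infer a material bias in favor of responders. Against this, PFS, EFS and DFS are exploratory and descriptive, and no comparison by consolidation is planned. With L = 6 the interval runs from about month 13.4–13.8 to month 18.0–18.4 after treatment start, so none of the landmarks (6, 9, 12 and 24 months) falls in it. Section 4.5.5.1 requires a full tumor assessment whenever progression is suspected, and a targeted examination is marked at the 3-monthly visits. FL follow-up CTs are themselves only six-monthly (Appendix 1 footnote kk). All of this stands and limits the consequence. Suspicion-driven imaging does not, however, time asymptomatic relapse.

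Finally, Section 3.1.6 and the opening of footnote e can be read as keeping post-treatment visits out of the consolidation period. On that reading the 3-month rule has no application, and nothing says when the first visit after consolidation is due.

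**Conclusion.** The point holds as an internal contradiction in Appendix 2. For every patient who completes consolidation, the first follow-up visit and CT are placed at about consolidation month 2.3 to 3.2. The interval from the EOC scan to the next CT is typically about 4 to 6 months, and the last-dose date decides it; the interval after the EOI scan without consolidation is 3 months. The intervals rest on the assumed last-dose month and shorten to 2.2 to 3.1 months if consolidation lasts 8 months.

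The consequence is limited to the timing of relapse detection in exploratory endpoints. CR at EOI is unaffected.

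The number of patients concerned cannot be derived. It is tempting to take 22 (55% of 40), but that is the assumed CR rate. Partial responders are also consolidated, and complete responders may leave for transplantation (Section 3.1.3). That the footnotes were simply left behind when consolidation was added is plausible but is an inference, since the preceding protocol version is not available; the point does not depend on it.

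**What to change.** Rewrite footnotes e and nn on the pattern of Appendix 1 footnote d.

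- Without consolidation: count visits and CTs from EOI, as now.
- With consolidation: count both from one common anchor, either the last dose or the EOC visit, with CT at 3 and 6 months and then six-monthly. Mixing the two anchors would put each CT 35 days away from its visit. The EOC anchor reproduces the 3-month spacing that other patients have after their EOI scan. The last-dose anchor puts the first CT 3 − 1.15 = 1.85 months after the EOC scan.
- Restrict the statement in footnote b about EOI closing treatment to patients who do not enter consolidation.

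The cost is three footnote edits in an amendment. Against the literal schedule it is roughly neutral in scans: the EOI + 3 and EOI + 6 CTs during consolidation go, and two after it come in.

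Separately, the consolidation length is 6 months in Table 7 and the Appendix 2 column header but up to 8 months in footnote c. These passages must be reconciled, because the intervals above depend on which applies.
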